### 7.5.2 Engagement with the Study and PILOT Intervention

For engagement with the study and with the PILOT intervention, the number of participants approached (from SCA form) and number who were willing to engage with PILOT peers, as well as the percent of those approached who were willing to engage, will be summarized. A 95% confidence interval will be provided for this percent. The length of engagement with PILOT will be similarly summarized. The template SAS code for these two analyses is given below:

```
proc freq data = secondout_consented;
  tables consented / binomial(level = 'Yes' CL = wald);
  weight count;
run;
```

where:

- *secondout\_consented* is the summarized dataset containing numbers of participants who provided or did not provide written informed consent to participate,
- *consented* is a categorical variable which has "Yes" and "No" responses, with "Yes" being consented to participate in the study (EC0107A.S07CNSNT or EC0107Y.S07CNSNT), and

- *count* is the number of participants who provided the corresponding response, out of patients approached for the study (SCA.SCNPTAPR).

This analysis generates the binomial proportion (with Wald confidence limits) for those consenting to be in the study.

```
proc means data = secondout_length mean std p25 p50 p75 min max clm;  
  var length;  
run;
```

where:

- *secondout\_length* is the dataset containing for each participant in PILOT treatment arm the days since randomization for each peer intervention,
- *length* is the number of days between the randomization date and the last intervention for that participant, as indicated on the PIL form in PILOT treatment arm (PIL.PIENGACT, PI2.P2ENGACT, ..., PI7.P7ENGACT).

This analysis generates descriptive summary statistics (mean, standard deviation, quantiles, and range) for the duration of engagement in the PILOT intervention.

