4.2 Study Rationale

For those with OUD, it is known that engagement in OUD treatment, longer retention in OUD treatment, and utilization of medication is associated with improved outcomes and decreased risk of subsequent overdose [9, 10]. After an NFOO, there is an initial increased likelihood of SUD treatment entry and utilization of buprenorphine. However, even at peak rates of treatment engagement – 11% at 1 month for SUD treatment engagement and 3% at 3 months for buprenorphine treatment – engagement is low and decreases with each additional month after overdose [12]. Moreover, given that less than half of the NFOO population identifies as having an

OUD, this low level of treatment entry and decline in treatment utilization over time raises the critical question of what treatment or risk reduction measures are appropriate for NFOO survivors, especially those for whom MOUD is not desired nor indicated, and how to improve the retention of those with SUD who enter treatment after an overdose [21, 22]. The proposed peer-led intervention being tested in this study (PILOT) has a distinct advantage in that it can assess and address overdose risk factors for those who survive an NFOO regardless of whether the individual identifies as having an SUD or is interested or ready for treatment entry.

Like similar programs [13-15, 17], FORCE has demonstrated remarkable preliminary success in observational evaluations, with linkage to treatment for 61% of participants in the first 18 months. As part of program evaluation for FORCE, in total, 235 overdose survivors have been approached, and 98% (n=230) agreed to participate in FORCE services, suggesting that recruiting overdose survivors from the ED utilizing this model is feasible. Fifty-eight percent of engaged clients (133/230) remained actively retained in FORCE at 9 months, defined as at least a monthly check in. Sixty-one percent (140/230) were linked with treatment or other recovery support services at some point in time during enrollment. Eight percent of engaged clients reported a return to any hospital “for any reason” (n=19), and 1.6% died of accidental overdose.

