### **3.1.5 Approached Population**

The approached population consists of all individuals who were approached in the ED for possible participation in the study, including those who did and did not provide verbal consent for further assessment of eligibility.

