**Table 36: Summary of Potentially Eligible Patients Willing to be Engaged over Number of Approached**

Number of Potentially Eligible Patients Approached 	Number of Participants Willing to be Enrolled 	Results 		
		Proportion	95% Lower Confidence Limit	95% Upper Confidence Limit
N	N	X.x%	X.xx	X.xx

 The number of participants approached is captured on the Screening Approach (SCA) form.

 Willingness to be enrolled is defined as providing verbal consent and is captured on the ENRA or ENRY enrollment form.

 Results are obtained from the Wald confidence limits.

Table 37: Summary of Length of Engagement and Enrollment in PILOT								
Number of Participants Enrolled in PILOT	Average Length of Engagement 					Results 		
	Minimum	25 th Percentile	Median	75 th Percentile	Maximum	Mean (SD)	95% Lower Confidence Limit	95% Upper Confidence Limit
N	X.x					X.x (x.x)	X.xx	X.xx

Length of engagement is calculated from the day of randomization to the last day a PILOT participant was assessed as “engaged” or “partially engaged” on the PIL form.

 Results are obtained from the Wald confidence limits.

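### The Wald interval planned for the percent willing to enroll covers too little if willingness is near 98%; a Wilson interval would be a free, minor improvement

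*SAP*

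**What the plan says.** The secondary engagement outcome compares the number of patients approached with the number willing to be enrolled (Protocol 7.2; SAP 7.4). For the resulting percent, SAP 7.5.2 promises: "A 95% confidence interval will be provided for this percent". Protocol 14.4 makes the same promise and names no method. The SAP supplies the method in its PROC FREQ template, "tables consented / binomial(level = 'Yes' CL = wald", and a sentence below the code again describes the limits as Wald. The Table 36 footnote states: "Results are obtained from the Wald confidence limits".

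The denominator is the approached population of SAP 3.1.5, "including those who did and did not provide verbal consent for further assessment of eligibility". Neither document says how many people will be approached or what share is expected to be willing. The one acceptance figure is in Protocol 4.2, from the FORCE program evaluation: "235 overdose survivors have been approached, and 98% (n=230) agreed to participate in FORCE services".

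**The concern.** The Wald interval takes its width from the observed proportion. When that proportion is close to 100%, the estimated standard error is too small and too variable, and the symmetric interval ignores the boundary. Actual coverage then falls below 95%, and the formula can give an upper limit above 100%. PILOT is a modified, manualized version of FORCE, and the protocol uses the FORCE acceptance figure to argue that recruiting in the ED is feasible, so a very high rate cannot be ruled out. At stake is how honestly the pilot's uncertainty about willingness is reported to those planning the larger trial.

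**Working it through.** **Inputs.**
- Confidence level 95%, z = 1.96 (SAP 7.5.2).
- Interval method Wald (SAP 7.5.2 and Table 36 footnote).
- Reference rate 230/235 (Protocol 4.2).
- Number approached n: not in the documents. Assumption: 150 to 1,000. About 150 is the floor, because about 150 are to be randomized (SAP 2.2.1).
- True willingness p: not in the documents. Assumption: 50% to 98%.

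**The documents' own figure.** 230/235 = 0.9787, which rounds to the stated 98%.
- Wald: 0.9787 ± 1.96 × √(0.9787 × 0.0213 / 235) = 0.9787 ± 1.96 × 0.00941, or 96.0% to 99.7%.
- Wilson for the same data: 95.1% to 99.1%.

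**Coverage formula.** Exact coverage is the sum of the Binomial(n, p) probabilities over every count x whose interval contains p.
- Wald interval: p̂ ± z√(p̂(1−p̂)/n).
- Wilson interval: [p̂ + z²/2n ± z√(p̂(1−p̂)/n + z²/4n²)] / (1 + z²/n).

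**One case in full: n = 150, p = 0.98.** The Wald interval contains 0.98 only when 2 to 8 people refuse. The probabilities of 2, 3, …, 8 refusals are 0.225, 0.226, 0.170, 0.101, 0.050, 0.021 and 0.008, which sum to 0.80. Most of the loss is 0 or 1 refusal (0.048 + 0.148 = 0.196), where the interval is too short to reach down to 98%.

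**Other denominators at a true 98%.**

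| Approached | Wald coverage | Wilson coverage | Chance Wald upper limit > 100% |
|---|---|---|---|
| 150 | 80.0% | 96.8% | 60% |
| 200 | 90.8% | 93.3% | 41% |
| 235 | 94.7% | 94.3% | 30% |
| 250 | 87.3% | 96.3% | 26% |
| 300 | 93.2% | 94.2% | 15% |
| 400 | 89.5% | 95.4% | 4% |
| 500 | 92.8% | 96.4% | 1% |
| 1,000 | 95.0% | 94.7% | <0.1% |

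Coverage oscillates with n, so single values mislead. Over every n from 150 to 300, Wald averages 89.3% (range 80.0% to 94.9%) and Wilson averages 95.5%.

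**Upper limit above 100%.** In the denominators checked this happens only with 1, 2 or 3 refusals. For example, 147/150 gives 0.98 + 1.96 × 0.01143 = 100.2%.

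**Other rates, average coverage over n = 150 to 300.**

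| True willingness | Wald | Wilson |
|---|---|---|
| 95% | 93.0% (minimum 89.4%) | 95.2% |
| 90% | 94.0% (minimum 92.2%) | 95.1% |
| 80% | 94.6% | 95.0% |
| 50% | 94.8% | 95.0% |

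At 90% the two intervals differ little: for 270/300, Wald gives 86.6% to 93.4% and Wilson 86.1% to 92.9%.

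**The case against.** The strongest reply is that the poor-coverage case may never arise here.

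- **The denominator.** Coverage near 80% needs only about 150 people approached. The denominator counts everyone approached, and about 150 must be randomized after preliminary screening, full screening and consent. The SAP's shell Table 1 provides for losses at each stage. A denominator of 150 would require almost no losses, so the real one should be larger. This stands.
- **The rate.** The 98% is uptake of a service in a program evaluation, not agreement to enter a randomized trial with follow-up to day 210. The protocol does not adopt it as an expected rate, and it provides for refusals through the Screening Exit Survey. This stands too, and at 90% or below Wald performs acceptably.
- **The numerator.** The Table 36 footnote says "Willingness to be enrolled is defined as providing verbal consent and is captured on the ENRA or ENRY enrollment form", while SAP 7.5.2 describes its dataset as holding "numbers of participants who provided or did not provide written informed consent to participate". Under written consent, ineligible people count as not consenting and the percent would move away from 100%. Under verbal consent a rate near 98% is more plausible. The inconsistency is separate from the choice of interval, could shift the estimate itself, and must be reconciled.
- **Use of the result.** The outcome is only summarized. No test or precision target is attached to it, and none of the four milestones in Protocol 7.4 uses it. This stands and limits the importance of the point.

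The reply does not give a reason to keep Wald. A larger denominator does not reliably cure the shortfall at a true 98% (89.5% at 400 approached), and on average over 150 to 300 approached Wilson is closer to 95% at every rate in the tables.

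**Conclusion.** The point holds as a minor one. If willingness is about 98%, the planned interval is not a 95% interval: over 150 to 300 approached it covers 89% on average. The shortfall is about two percentage points at 95% willingness and about one or less at 90% and below. These figures rest on assumed denominators and rates, because the documents state neither.

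A reader might infer that the interval will cover only about 80% in this trial, or that it will report an impossible upper limit. The documents do not support either reading. The 80% belongs to the smallest conceivable denominator. An upper limit above 100% needs one to three refusals, and the cited 230/235 itself gives 99.7%. Nor is any feasibility conclusion invalidated, since none is tied to these limits. Wilson is not better at every single n either: at a true 98% Wald is marginally closer to 95% at 235 and at 1,000. The case for Wilson is that it stays close to 95% without anyone having to predict the rate.

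**What to change.** In SAP 7.5.2, change `CL = wald` to `CL = wilson` in the PROC FREQ template. Change the sentence below the code that names Wald limits, and the Table 36 footnote, to match; leaving either would create a new inconsistency. The identically worded Table 37 footnote concerns mean length of engagement, not a proportion, and is not part of this change.

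The cost is one keyword and two short text edits. The protocol needs no change, because it names no method. In the same revision, state whether the numerator is verbal or written consent, and use that definition in SAP 7.4.2, 7.5.2 and Table 36.

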7.2 Secondary Outcome Measures

The secondary outcomes of the study are: 1) number of steps achieved on a modified SUD Cascade of Care at 180 days (6 months) after Index ED admission; and (2) engagement with the study and PILOT intervention, measured by (a) the number of potentially eligible patients approached compared with the number willing to be enrolled and (b) the length of engagement and enrollment in PILOT among those randomized to PILOT. Length of engagement and enrollment is defined as the time from baseline to last meeting with the PILOT intervention/counselor.

Modified SUD Cascade of Care (Secondary Outcome Measure):

CASCADE	OD Identification & Harm Reduction	Engagement in Care		MOUD Initiation	MOUD Retention			Treatment Response & Remission (6 month)		
STEPS	1 ↑ Harm Reduction	2 Any Care	3 Regular Care	4 Any MOUD	5 MOUD X 1 mo	6 MOUD X 3 mo	7 MOUD X 6 mo	8 ↓ SUD Severity	9 Early Remission	10 ↑ Recovery Score
MEASURE	Harm Reduction Checklist	Step 2-7 Assessment Form (SAF 2-7)		SAF 2-7	SAF 2-7 AND MOUD Confirmation Form			DSM 5 Checklist Toxicology screen		Assessment of Recovery Capital Scale

Step Eligibility: All enrolled participants will be considered to have 0 steps achieved at the time of study entry (baseline). Acknowledging that individuals will vary in presence and types of SUD diagnoses, this pilot trial will evaluate the differing numbers of steps achieved in each sub-type of enrolled participant (primary OUD, primary SUD other than OUD, no identified SUD identified at baseline via administration of the DSM-5 checklist). A participant will be counted as having met a particular step if criteria are met at ANY study visit or for any length of time during the study, even if the participant subsequently does not endorse a previously endorsed item.

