1. Number of steps achieved on the modified SUD Cascade of Care
2. Number accepting the intervention (to possibly engage with CPPSs using the PILOT model) compared with number approached
3. Length of time from baseline to last meeting with the PILOT intervention/counselor

Participants will be recruited at each ED site. Research staff assigned to the study will work during times to include evenings and weekends to ensure success with enrollment. Research staff will identify patients seen in the ED by screening, reviewing the ED trackboards, and by provider or peer referral. A member of the research team will keep a log of all patients screened and excluded and the reasons for exclusion. Potential participants identified will be evaluated by research staff for eligibility.

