### **6.2 Treatment Exposure**

PILOT peers are expected per the PILOT Peer Intervention Manual (v0.1) and training to attempt to contact participants in the active intervention PILOT treatment arm once a week at a minimum during the treatment period. More frequent contact may be needed depending on the individual participants' needs and engagement. The Peer Intervention Log (PIL) form captures the intervention delivery by the PILOT peer and is expected daily until the participant reaches end of treatment. PILOT participant engagement category is assessed by the peer on the first day of each 7-day period throughout the intervention. Participants in the TAU treatment arm are not assessed for treatment exposure.

Treatment exposure will be summarized in the ITT population for the PILOT intervention arm as a) descriptive statistics for the number of contacts attempted (PIENGACT = '01') and the number of contacts completed (PIENGACT in ('01', '02')), treated as continuous variables, by site and engagement category (PICURENG), and b) the number of days of engagement by site, study period (30-day intervals), and time spent by peers engaging (PITOTLTM; categorical).

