#### **7.4.2 Engagement with the Study and PILOT Intervention**

The assessment of whether recent NFOO survivors within an ED setting are willing to engage with peer support services will be measured by (a) the number of potentially eligible patients approached (Screening Approach form; SCA) compared with the number willing to be enrolled (provided verbal consent; ENRA or ENRY form), and (b) the length of engagement and enrollment in PILOT among those willing to be enrolled and randomized to PILOT. The length of engagement will be calculated from the day of randomization to the last day a PILOT participant was assessed as “Engaged” or “Partially Engaged” on the PIL form.

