**Table 19: Summary of Treatment Exposure in PILOT Intervention: Contacts by Site and Engagement Category**

Site		Engagement Category 				Overall Engaged 
		Missing	Unengaged	Partially Engaged	Engaged	
Site 1	Number of contacts attempted 	N				
	Number of contacts attempted per participant per week					
	Mean	XX				
	SD	xx.x				
	Min	XX				
	25 th Percentile	XX				
	Median	XX				
	75 th Percentile	XX				
	Max	XX				
	Number of contacts completed 					
	Number of contacts completed per participant per week					
	Mean					
	SD					
	Min					
	25 th Percentile					
	Median					
	75 th Percentile					
	Max					
Site 2						
Site 3						
Total						

 Engagement category was assessed on the first day of the 7-day period on the Peer Intervention Log (PIL).

 Overall engaged includes partially engaged and engaged.

 Contacts attempted and completed was captured daily on the PIL.

**Table 20: Summary of Treatment Exposure in PILOT Intervention: Time Spent Engaging in Intervention Activities by Site and Intervention Period**

Site	Study Period	Missing	Time Spent Engaging in Intervention Activities 						
			No time spent (0 minutes)	1 - <15 minutes	15-30 minutes	31-45 minutes	46-60 minutes	> 1 hour	Overall 1+ minutes
Site1	Day 1 – 30	N (X.x%)	N (X.x%)	N (X.x%)	N (X.x%)	N (X.x%)	N (X.x%)	N (X.x%)	N (X.x%)
	Day 31 – 60	...							
	Day 61 – 90	...							
	Day 91 – 120								
	Day 121 – 150								
	Day 151 – 180								
	Day 181 – 210 								
	Total	...							
Site 2	...								
Site 3	...								
Total	...								

 Time spent engaging in intervention activities was captured daily on the Peer Intervention Log (PIL).

 PIL entries through the end of the follow-up visit window (Study Day 225) are included in the final intervention study period.

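### Length of engagement in PILOT, a secondary outcome, has three different end points, and the one tied to variables in SAP 7.5.2 has no filter to keep out unanswered contact attempts

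*SAP*

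**What the plan says.** The documents give three end points for one outcome.

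- **Protocol 7.2:** "Length of engagement and enrollment is defined as the time from baseline to last meeting with the PILOT intervention/counselor". Protocol 14.1.1 repeats it in the list of outcome measures: "Length of time from baseline to last meeting with the PILOT intervention/counselor".
- **SAP 7.4.2:** the length is "calculated from the day of randomization to the last day a PILOT participant was assessed as “Engaged” or “Partially Engaged” on the PIL form". The footnote to the Table 37 shell follows the same rule ("Length of engagement is calculated from the day of randomization to the last day a PILOT participant was assessed as" engaged or partially engaged).
- **SAP 7.5.2:** the analysed variable "is the number of days between the randomization date and the last intervention for that participant, as indicated on the PIL form". The variables named are PIENGACT on the first-day log through P7ENGACT on the seventh-day log. No code values are given.

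SAP 6.2 shows what PIENGACT holds. Treatment exposure is to be summarized as "the number of contacts attempted (PIENGACT = '01') and the number of contacts completed (PIENGACT in ('01', '02"'). The engagement rating is a different variable, PICURENG, recorded on the first day of each 7-day period.

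Three other provisions bear on how the log fills up. Peers are expected to attempt contact at least weekly during the treatment period, and the log is expected daily until end of treatment (SAP 6.2). For participants lost to follow-up, end of treatment is dated to the peer's final contact attempt (SAP 6.1). The log covers contacts attempted as well as connected, with the participant or with family and support persons (Protocol 11.11.1).

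**The concern.** Two programmers following the SAP could produce different results for the same table. One would use the weekly rating (7.4.2 and the Table 37 footnote), the other the activity codes (7.5.2), and neither is tied to the protocol's last meeting. As the SAP stands, Table 37 would carry a footnote that the 7.5.2 variables do not implement.

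The 7.5.2 route has a further weakness. With no code filter, the last entry in the log for someone who has stopped answering may be an unanswered attempt. Continued outreach to non-responders is part of the PILOT model, so such entries are to be expected, and they belong to the participants whose disengagement this outcome should show. Feasibility of engagement is a stated purpose of the pilot and is meant to inform the larger trial (Protocol 6.2), so a length that partly measures peer effort would mislead that planning.

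**Working it through.** The documents state no expected value for this outcome, so there is no figure to reproduce. The check has three parts.

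**1. Definitions side by side**

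| Source | Start | End | Variable |
|---|---|---|---|
| Protocol 7.2, 14.1.1 | Baseline | Last meeting with the peer | Not named |
| SAP 7.4.2, Table 37 | Randomization | Last Engaged or Partially Engaged rating | Rating on the log (PICURENG in 6.2) |
| SAP 7.5.2 | Randomization | Last intervention | PIENGACT to P7ENGACT, no codes |

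The end points differ in kind: an event, a weekly judgement and a log entry. The difference in start is minor. Baseline and randomization usually fall at the same visit, although the baseline window in SAP 3.2.2 runs to Day 7.

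**2. Code mapping in SAP 6.2**

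Attempted = {01}. Completed = {01, 02}. Since {01} is contained in {01, 02}, every attempted contact is also counted as completed, and completed can never be fewer than attempted. The two look reversed. The filter missing from 7.5.2 therefore cannot be borrowed from 6.2 as written. The same mapping feeds Table 19.

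**3. Illustration of size (assumed response patterns)**

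*One participant.* Weekly attempts from Day 0, last answered on Day 56. Length is 56 days by last completed contact. By last attempt it is 84 days if attempts stop at Day 84, and 175 days if they run to Day 180 (25 × 7 = 175).

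*Arm level.* A share *s* stops answering at a time R uniform over Days 0-180, and the rest answer to Day 180. Outreach continues *k* days after the last answer, cut at Day 180.

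- Mean by last completed contact: 180(1 − s) + 90s = 180 − 90s.
- Overstatement by last attempt: s × E[min(k, 180 − R)] = s × (k − k²/360).
- The bracket is 30 − 900/360 = 27.5 for k = 30, 60 − 3600/360 = 50 for k = 60, and 180 − 32400/360 = 90 for outreach to Day 180.

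The middle value of *s* is the complement of FORCE retention in Protocol 4.2: 133/230 = 57.8%, so s = 0.422. It is an anchor only, because that figure is for 9 months in a program evaluation. The values 0.20 and 0.60 bracket it.

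| s | Last completed contact | Outreach +30 days | Outreach +60 days | Outreach to Day 180 |
|---|---|---|---|---|
| 0.20 | 162 | 167.5 (+5.5) | 172 (+10) | 180 (+18) |
| 0.422 | 142 | 154 (+12) | 163 (+21) | 180 (+38) |
| 0.60 | 126 | 142.5 (+16.5) | 156 (+30) | 180 (+54) |

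If outreach ends with the last answered contact (k = 0), or only completed contacts are used, the overstatement is zero for every *s*.

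**The case against.** The strongest reply is that SAP 7.5.2 speaks of the last intervention, not the last log entry. Protocol 11.11.1 separates contacts attempted and connected from interventions performed, so an unanswered call is not naturally an intervention. Read that way, 7.5.2 comes close to the protocol's last meeting. This stands as a possible reading, and the PIENGACT code list is not in the documents. But no filter is written, and the variable named is one that 6.2 also uses for attempts.

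A second reply is that 7.4.2 and Table 37 agree with each other and would not count outreach to someone rated Unengaged. That is true, and it limits the outreach problem to 7.5.2. It does not remove the conflict within the SAP or with the protocol.

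Three stronger readings are tempting but unsupported.

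- *Length will approach 180 days whatever participants do.* This needs weekly pursuit of every non-responder to Day 180. SAP 6.1 provides for treatment ending earlier, and Table 18 lists refusal, withdrawn consent, moving away and death among the reasons. Values near 180 are the extreme of the range.
- *Late log entries stretch the length beyond the intervention.* The footnote saying "PIL entries through the end of the follow-up visit window (Study Day 225) are included in the final intervention study period" belongs to Table 20, on time spent by study period. It does not govern Table 37.
- *A Day 180 cap, a zero score for no contact, or exclusion of family-only contacts is what the protocol means.* Protocol 7.2 contains none of these rules.

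It is also fair that the outcome is descriptive and single-arm, that none of the four pilot milestones in Protocol 7.4 uses it, and that Tables 18 to 20 show disengagement in other ways (Table 19 only once its codes are corrected).

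**Conclusion.** The inconsistency is certain from the text: three end points, and a Table 37 footnote that the 7.5.2 variables do not implement. The SAP 6.2 mapping is also certain as written to count every attempt as completed; that the codes were swapped is the likely explanation, not an established one.

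The inflation of length by unanswered outreach is possible, not shown. It depends on 7.5.2 being the rule followed, on no filter being applied, and on attempts continuing after the last answered contact. Under those conditions and the assumed response patterns, the mean is overstated by about 5.5 to 54 days with 20-60% stopping, and by 12, 21 or 38 days with 42% stopping. Without them it is zero. The effect is on the feasibility result in about 75 PILOT participants (150 randomized 1:1). The primary test and its power are untouched. This should be corrected before the analysis, since choosing among three definitions after seeing the data would weaken the feasibility claim.

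**What to change.** 1. Use one definition in SAP 7.4.2, SAP 7.5.2 and the Table 37 footnote, following the protocol: days from baseline/randomization to the last completed contact (meeting) between the participant and the PILOT peer. State the start day once.
2. In 7.5.2, name the PIENGACT to P7ENGACT codes that count, and exclude attempt-only entries.
3. Check the SAP 6.2 mapping against the form's code list and correct it so that completed contacts are a subset of attempted contacts. Table 19 then follows.
4. Keep the peer-rated engagement category as a descriptive supplement.
5. If a cap at Day 180, a zero for participants with no completed contact, or exclusion of family-only contacts is wanted, write it as an added rule and not as the protocol's definition.

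The cost is SAP wording and a code filter, with no new data. The reported mean length may be lower than under an unfiltered derivation.
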